Project 1--Long-Term Outcomes of Delirium, Leader: [name].: This study will test the hypothesis that delirium will be independently associated with a higher rate of long-term cognitive and functional decline. We will utilize appropriate epidemiologic and statistical approaches to evaluate the impact of delirium on cognitive functioning in our prospective cohort over time, as reflected by our composite summary neuropsychological measure, as well as long-term functional decline and health care utilization. Importantly, these analyses will control for relevant covariables, including age, gender, education, cognitive reserve indicators, APOE-ε4 status, comorbidity, baseline cognitive impairment, and vascular risk factors, on which detailed information will be collected for this study. A sub-study of project 1 will look at the clinical outcomes of delirium, specifically rates of conversion to mild cognitive impairment (MCI) or dementia, among those who demonstrate significant cognitive decline during the study. A validation-study of project 1 will validate phone neuropsych testing with face-to face neuropsych testing. The phone version of the neuropsych testing may be used in the future for patients who are not available for face-to-face interviews. Another sub-study to Project 1 will identify markers of under- and over treated pain and associated adverse outcomes including delirium and prolonged length of stay during the index hospitalization using existing SAGES data and chart review methods to collect additional data.

Project 2--Biomarker Discovery for Delirium, Leader: [name].: The goal of this study is to utilize state-of-the-art methods toward the discovery of plasma biomarkers for delirium. Plasma biomarkers will be assessed at 4 time points for this study: baseline, immediately post-operative, hospital day 2, and one-month follow-up. The Luminex multiplex analyzer system will be used to describe a cytokine “signature” associated with delirium. Mass spectrometry proteomics will be used to describe a plasma protein “signature” for delirium. We will also examine the relationship of the cytokine and protein signatures

with long-term cognitive and functional outcomes following delirium. Finally, we will create a repository of plasma and genetic material, which will be used for future biomarker discovery and validation studies for delirium and other surgical outcomes.

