We will also examine a non-surgical comparison group, which will be at low risk for hospitalization, and will be matched with the surgical group. Other than surgery, they will meet all other inclusion and exclusion criteria for the surgical group. The purpose of the group is to help us evaluate the cognitive trajectory in the absence of hospitalization, surgery, and delirium and to quantify retest (learning) effects. For this group, we will enroll 120 primary care patients from BIDMC, who will be frequency matched (using a prospective frequency matching algorithm) to the surgical group on age, gender, education, baseline cognitive function, and comorbidities (i.e., both vascular and nonvascular comorbidities). We have successfully implemented this type of prospective matching in our pilot work and previous studies (*Charpentier 2001*).

For Project 5, we will enroll current SAGES patients (n=100). Interim analysis of data collected from the current SAGES study has identified a need for additional biomarkers and other neurophysiologic measures to complement and further the work done thus far in SAGES. With this feasibility study we want to evaluate if SAGES participants would be willing to undergo additional procedures.

Project 6: For this project, the Fried frailty index (*Fried 2000*) will be utilized to identify contrasting aging phenotypes (frail and robust/non-frail) in the SAGES I original sample. 1. We will enroll current SAGES I participants (up to n=30) to identify 15 frail and 15 robust/non-frail individuals, and to obtain fresh blood specimens to develop iPSC cell lines (5 per participant). 2. We will utilize the iPSC cell lines

to probe various molecular-physiologic differences between the frail and non-frail samples in 4 different labs:

- a) Neurophysiology: The [name] lab will differentiate the iPS cells into neurons and probe neurophysiologic differences
 - b) Muscle function: The [name] lab will differentiate the iPS cells into muscle cells and probe physiologic differences at the molecular level
 - c) Mitochondrial function: The [name] lab will explore differences in mitochondrial functioning, applying metabolomic and other molecular approaches
 - d) Nicotinamide adenine dinucleotide (NAD) function: The [name] lab will explore differences in oxidative functioning particularly in relationship to NAD functioning.
3. We will develop and validate a human platform to further examine frailty in vitro in future larger studies

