A.3.1.3. Baseline assessment interviews: The purposes of the baseline assessment are to describe the subjects, to document baseline neurocognitive function, to characterize baseline risk factors for delirium and cognitive decline, and to measure potentially confounding factors. This assessment will be conducted immediately following the screening assessment in eligible patients. The 80-minute baseline interview will collect information on cognitive functioning (neuropsychological test battery), demographics, education, occupation, medical diagnoses, comorbidity, medications, health habits (e.g., smoking, alcohol), hearing, mobility, basic and instrumental activities of daily living, depression, and anxiety. In a pilot study, we have verified that these interviews are feasible and tolerable in older persons. A family or caregiver interview will be conducted to establish the subject's baseline cognitive functioning, to assess for evidence of dementia [DQ (*Silverman 1987*)], and to determine any recent changes in mental status. Based on our previous and pilot studies, about 3-4% of participants will not have a family member or caregiver available to participate in these interviews; in these cases, we will approach (with the patient's consent) friends, neighbors, visiting nurses, or other reporters about the patient's baseline functioning. All enrollment and baseline assessments will be completed prior to the scheduled surgical admission.

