A.10.1 Subject Selection: The frail group will be selected as the most frail in the remaining SAGES I orthopedic surgery population (scores of 4-5), with gradually progressive trajectory over follow-up. The non-frail (robust) group will be selected as those without frailty indicators (scores of 0-1) with generally non-frail scores over all follow-up periods (scores of 0-2, and remaining at score=0 at final follow up). We will select participants to have mean age as close as possible between the frail and non-frail groups.

A.10.2. Instruments, procedures and blood acquisition: We will utilize the frailty questions and assessments that are already in our assessment battery and described above, including weight & height, SF 12 questions, Minnesota leisure time, grip strength and timed walk.

We conduct an additional frailty assessment and will collect in total 20ml blood from each participant. Blood samples will be collected into sterile vacuum tubes using either a vacutainer or butterfly system, at the preference of the phlebotomist. Blood will be drawn by a trained member of our research team.

12 ml of the blood will be delivered to the Harvard Stem Cell Institute (HSCI) iPS Core Facility is a service center located in [name] that we will contract with for the derivation of iPS cell lines from the donor samples.

8 ml of blood will be delivered to the CRC at BIDMC

All samples provided to the iPS Core or BIDMC for derivation will be coded. The iPS Core and study investigators will never receive any donor identifiable information. The iPS Core and BIDMC CRC will use their standard operating procedures and protocols for derivation and characterization services provided.

B. Statistical Considerations

B.1. Sample Size Justification:

Our sample size was chosen based on an iterative process involving determining the size of the target population eligible, feasibility constraints, and then verifying adequate power to test the hypotheses across all of our proposed studies, Projects 1-4. Through these detailed considerations, and input from our expert statisticians, we have been able to verify adequate power to address all of our study aims with the proposed sample sizes of 550 surgical patients and 120 non-surgical controls. We have presented power calculations for each of primary aims of the studies below. Power has similarly been verified for all aims of each project.

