B.1.5. Sample Size for Project 5. For the Feasibility Interview, the sample size of 100 was selected to enable robust estimates of the percent of SAGES participants willing to undergo these procedures.

B.1.6. Sample Size for Project 6. Due to budgetary constraints of generating the cell lines and running assays across 5 laboratories, we will include a convenience sample of only up to 30 orthopedic surgery participants (~15 frail and ~15 non-frail) for this pilot study.

B.2. Data Analysis.

The Data Management and Statistical Analysis (DMSA) Core (Core C) will provide data management services, statistical analyses and collaboration to the other Cores and Projects in the Program Project. The primary responsibilities of the DMSA Core will be to develop information systems and software for tracking participants, receiving, management and cleaning of data, generation of data sets, and performing statistical analyses tied to the specific aims of the projects. The specific aims for this Core are: 1. To generate information systems and software for tracking participants and flow of data; 2. To assemble and manage a database of longitudinal information collected from participants during screening, follow up and the conduct of individual projects; 3. To collaborate with the Epidemiology Core and Project Leaders in all phases of study design including determining the sampling scheme for the study, addressing non-response and providing real-time selection, enrollment, and matching as needed for substudies (Project 3); 4. To provide methodologic and analytic expertise to Project Investigators including study design and conduct, development and implementation of data analytical plans, interpretation of statistical results and manuscript preparation; 5. To lead analyses of variables collected by the Epidemiology Core and individual research projects; and 6. To develop composites for cognition and functional outcomes. Senior leadership for the Core will be provided by L. [name], Professor and former Chair of the Department of Biostatistics at Boston University School of Public Health. Day-to-day and operational leadership will be provided by [name], located at the Institute for Aging Research (IFAR) of the Hebrew Rehabilitation Center (HRC). [name] (BIDMC) will also serve as coinvestigator and member of this Core. Data will be stored and analyzed at the Hebrew Rehabilitation Center.

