Table 3 provides a brief description of each Project's hypotheses and a general indication of the analytic approach. Projects 1-4 have hypotheses that involve change, including change in binary variables (occurrence of delirium, a non-absorbing state) or change in cognition. A general approach to the analysis of longitudinal data of this kind is the general linear mixed model (GLMM). Survival models (e.g., Cox proportional hazards, frailty, and discrete time survival models) could also be used for binary events if they are assumed to be absorbing (e.g., time to first delirium). Parameters for such models can be estimated with a variety of different software packages to yield varying classes of models used for change studies: individual growth curve models; random coefficient models; multilevel models; mixed models; or hierarchical linear models.

We will consider several approaches to account for missing data in our study, including maximum likelihood methods that model the missingness and imputation. One approach uses a random effects model for the outcome measurement, where the random effect represents the subject-specific effect. A second possible approach is the random-coefficient selection model that allows subject drop-out to depend on missing values of the outcome variable. Still another approach will be multiple imputation methods. Applying these multiple methods will allow us to assess the degree to which our inferences are robust to different methods for handling missing data. If findings are consistent across methods, we will be reassured about the robustness of our findings. If findings are not consistent, then these multiple methods allow us to further explore the inconsistency and to decide on the best approach.

Project 5 data will be analyzed using summery and descriptive statistics.

Project 6 data will be analyzed at the following 5 Harvard labs:
Neutrons: [name] lab will differentiate the iPS cells into neurons and probe neurophysiologic differences. Muscle cells: The [name] lab will differentiate the iPS cells into muscle cells and probe physiologic differences at the molecular level. Mitochondrial function: The [name] lab will explore differences in mitochondrial functioning, applying metabolomic and other molecular approaches.

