See **Section A.5.1** for selection of MRI substudy patients. Additional exclusions for the MRI substudy are any contraindication to MRI which may include the following: 1. Pacemaker; 2. MRI incompatible metal implant; 3. Recently implanted vascular clip; 4. History of claustrophobia; 5. Metal fragment within the eye. Because of the age-range of our study population (age 70 and older), there will not be any pregnant women in our sample.

C.1.3. Non-surgical Comparison Group: Other than the requirement for surgery, the comparison group will meet the same inclusion and exclusion criteria listed above. The comparison group will also be matched to the surgical cohort using a computerized prospective frequency-matching algorithm for age, gender, education, baseline cognitive function, and comorbidities. Success of matching will be monitored regularly, and adjustments for imbalances will be made.

C.2. Inclusion of Women, Minorities, and Children: Gender and minority representation will be present in the study sample-projected enrollment figures are presented below. We will put into place steps to enhance minority recruitment and retention. In our previous work, the investigators have been able to recruit a study sample of similar racial/ethnic background to the overall eligible population. Children will not be included in the sample, since the study is designed to examine cognitive outcomes in older adults. In addition, because of our targeted elderly age group, no women of childbearing age will be included in the sample.

Project 6 inclusion: up to 30 orthopedic surgery participants from the SAGES study (15 frail and 15 non-frail) will be selected for this pilot study. Initial eligibility will be established by SAGES participants frailty status from previous frailty assessments. Then eligible participants who previously gave permission to be approach for other studies, who passed the SAGES capacity assessment and who provide written consent for this sub-study will be included and another frailty assessment will be performed. If the current frailty status is within the eligibility range described previously phlebotomy will be performed.

TARGETED/PLANNED ENROLLMENT: Number of Subjects			
Ethnic Category	Sex/Gender		
	Females	Males	Total
Hispanic or Latino	11	3	14
Not Hispanic or Latino	341	245	586
Ethnic Category: Total of All Subjects *	352	248	600
Racial Categories			
American Indian/Alaska Native	0	0	0
Asian	2	2	4

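### Project 6 balances its frail and robust donors on mean age only; adding the number of women to the selection rule would cheaply remove an avoidable source of confounding

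*Protocol*

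**What the plan says.** - **Group sizes.** Section A.2 of the protocol plans "to identify 15 frail and 15 robust/non-frail individuals". Section B.1.6 presents this as a budget-limited pilot: "we will include a convenience sample of only up to 30 orthopedic surgery participants (~15 frail and ~15 non-frail) for this pilot study".
- **Contrast.** The cell lines are to be used "to probe various molecular-physiologic differences between the frail and non-frail samples in 4 different labs" (A.2). A further laboratory runs an inflammatory index to confirm that the frailty phenotype was correctly identified.
- **Balancing rule.** Section A.10.1 chooses donors by frailty score and trajectory, then adds: "We will select participants to have mean age as close as possible between the frail and non-frail groups". Sex is not mentioned.
- **Eligibility.** Under C.2, "Initial eligibility will be established by SAGES participants frailty status from previous frailty assessments". Permission, capacity, written consent and a repeat frailty assessment follow. None of these steps concerns sex.
- **Analysis.** Section B.2 says "Project 6 data will be analyzed at the following 5 Harvard labs" and lists the laboratories and assays, without naming a test or covariates.
- **Sex is already known.** Section A.3.1.3 states: "The 80-minute baseline interview will collect information on cognitive functioning (neuropsychological test battery), demographics, education, occupation". For Project 1, section B1 states that "these analyses will control for relevant covariables, including age, gender, education, cognitive reserve indicators" and further factors. Sections A.2, A.3 and C.1.3 match the non-surgical comparison group to the surgical cohort on gender, among other factors.

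**The concern.** By balancing age, A.10.1 accepts that a demographic difference between the donor groups could be mistaken for a frailty difference. It does not apply the same care to sex. The protocol controls gender in its larger comparisons but leaves it free in its smallest one, where a difference of a few donors matters most.

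The frail against robust contrast is the whole purpose of the pilot. If the groups differ in sex mix and an assay differs by sex, part of an apparent frailty signal would be a sex signal, and the same could distort the inflammatory check on the phenotype. The cell lines are meant to be kept and eventually banked (B.2), so an imbalance among the donors would stay in the resource. A later analysis can adjust for who was sampled, but cannot change it.

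**Working it through.** The protocol states no power, effect size or error rate for Project 6, so there is no figure to reproduce. What follows illustrates size.

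**Inputs from the protocol**
- 15 donors per group (A.2; approximate in B.1.6).
- Planned enrolment of 352 women among 600 (table in C.2): 352/600 = 58.7%. This describes the whole planned study. The sex mix of the remaining orthopedic participants at the two frailty extremes is not given.

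**Assumptions**
- Sex difference in an assay: s, in within-sex SD units.
- Numbers of women per group: 12 v 6 and 11 v 7 as imbalanced cases, 9 v 9 as a balanced one.
- No true frailty effect, and an unadjusted two-sided 5% t-test.

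**1. Bias of the unadjusted contrast** = (difference in proportion of women) × s. With s = 1:
- 12 v 6: (12 − 6)/15 × 1 = 0.40 SD.
- 11 v 7: (11 − 7)/15 × 1 = 0.27 SD.
- 9 v 9: zero for any s.

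**2. False positives of the unadjusted test** (simulation, at least 40,000 runs per case; ranges cover repeat runs). With s = 1:
- 12 v 6: 13.5% to 14.2%.
- 11 v 7: 7.1% to 7.5%.
- 9 v 9: about 3%. This is below 5% because the sex difference widens the spread within each group.

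At 12 v 6 with s = 0.5, the bias is 0.20 SD and the rate 7.6%.

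**3. What adjustment for sex does.** The unadjusted standard error, for known sex mix, is √(2/15) = 0.365 SD. With sex as a covariate it is 1/√W, where W sums (frail × robust)/(frail + robust) over women and men.
- 12 v 6: W = 12×6/18 + 3×9/12 = 4.00 + 2.25 = 6.25, so 0.400 SD. Ratio 0.400/0.365 = 1.10.
- 11 v 7: W = 11×7/18 + 4×8/12 = 4.28 + 2.67 = 6.94, so 0.379 SD. Ratio 1.04.
- 14 v 6, one group nearly single-sex: W = 14×6/20 + 1×9/10 = 4.20 + 0.90 = 5.10, so 0.443 SD. Ratio 1.21, with the whole comparison among men resting on one frail donor.

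In simulation at s = 1, adjustment brings the 12 v 6 bias to 0.00 and rejection to 5.0%; at 11 v 7 rejection is 4.7%. Power for a 1.06 SD frailty effect, about 80% at 15 v 15, falls to about 72% at 12 v 6.

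**4. How often imbalance arises by chance.** If both groups were drawn at 58.7% women (two independent binomials of size 15), the counts of women differ by 3 or more with probability 35.4%, by 4 or more with 19.3%, and by 6 or more with 4.0%. Over repeated draws of this kind the unadjusted test stays at about 5%, because chance imbalance adds noise and no systematic bias.

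**5. If sex and frailty are associated** (assumed 70% v 50% women), a gap of 4 or more has probability 43.6%. With s = 1 the bias is 0.20 × 1 = 0.20 SD and false positives are 7.9%. At 80% v 40% the figures are 84.7%, 0.40 SD and 16.2%.

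**The case against.** The strongest reply is that the bias appears only if the analyst ignores a variable already on file. B.2 prescribes no test for Project 6, covariates are commonly left to an analysis plan that is not shown here, and adjustment removes the bias in the cases above. This stands. A reader might infer that the imbalance could not be repaired afterwards. The calculation does not support that at 12 v 6 or 11 v 7, where the cost is 10% or 4% in standard error. Adjustment becomes fragile only when a group is nearly single-sex.

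A reader might also infer that a serious imbalance is likely. The protocol does not show it. At the planned sex mix, a gap as large as 12 v 6 has a 4% chance. A systematic gap needs a link between sex and frailty among these candidates, and the protocol gives no figure for one, nor for any sex effect on the assays.

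Finally, this is a convenience sample with tight frailty criteria, a repeat assessment and no stated pool size. Strict one-to-one matching on sex and individual age could be hard to fill and could lose pairs if a donor or cell line fails. That counts against strict pairing, but not against balancing the number of women.

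What the reply does not answer is timing. The selection rule belongs to the protocol and takes effect before any blood is drawn. Balance at that stage avoids the loss of precision and the reliance on small sex strata.

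**Conclusion.** The point holds as a modest design improvement. A.10.1 balances mean age only and leaves sex free, although sex is known for each candidate and gender is a matching factor elsewhere in the same protocol. The omission contradicts nothing in the text, and no Project 6 result is shown to be confounded.

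The illustrative size is a bias of 0.40 SD with about 14% false positives for an unadjusted contrast at 12 v 6 women, and 0.27 SD with about 7% at 11 v 7. Both rest on an assumed sex effect of 1 SD and an assumed sex mix. With sex in the model the bias goes, and what remains is lost precision, plus fragility if a group is nearly single-sex. Project 6 is a pilot of up to 30 donors, and no main SAGES outcome depends on it.

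**What to change.** Change the balancing sentence in A.10.1 so that donors are selected to bring both mean age and the number of women as close as possible between the frail and non-frail groups. Where the pool allows, choose robust donors to fit the sex mix of the frail donors. Report sex by group with the results. Strict pairing is not needed.

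The cost is one clause in the protocol and possibly a slightly looser age match. Sex is already recorded, so no new data are needed. With equal numbers of women the bias from sex is zero whatever the size of the sex effect.

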We proposed a 7 year prospective observational study which got extended to 12 years, including 6 months for initiation, 30 months for patient enrollment, 42 months (additional) to complete all patient follow-ups, and 6 months for statistical analyses and manuscript preparation. The proposed study will enroll 550 elective non-cardiac surgical patients, each of whom will be followed prospectively for a minimum of 18 months and up to 72 months initially and then extended to 12 years, after their initial hospitalization. All patients will undergo a baseline evaluation prior to hospitalization, including neuropsychological and frailty testing. The primary outcomes for this project are cognitive decline, based on a neuropsychological test battery, and functional decline. When admitted for the index hospitalization, patients will be assessed daily for the development of delirium, the major predictor variable. Subsequently, each patient will be followed prospectively for a minimum of 18 months or until death or termination of the project period with a face-to-face interview at 1 and 2 months, telephone interviews at 4, 9, 15, 21 and 27 months and face-to-face interviews including neuropsychological testing every 6 months up to 12 years. Medical records for each patient from all hospitalizations (including outside hospitals) will be reviewed at the end of their index hospitalization, after each subsequent hospitalization, after their final study **interview or end** of data collection (12 years)--to identify any hospitalizations (including recurrent delirium and repeat surgeries), intercurrent illnesses, new diagnoses, unidentified hospitalizations, or unreported deaths.

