B.1.1. Sample Size for Project 1. For Project 1 (epidemiologic outcomes study), the power calculation for our primary outcome (cognitive decline by our summary cognitive measure) was examined as follows. Hypothesis 1 tests whether the degree of cognitive decline is higher in the delirium group, compared with the non-delirium group at 18 months. Estimates of effect sizes are drawn from Francis et al. (Francis 1992) who found that a sample of delirious patients declined over 2 years on MMSE performance from a baseline mean (SD) of 27 (3.3) to 23.7 (5.1), while a control sample declined from a baseline mean of 27 (2.4) to 26.4 (4.2). The net decline attributable to delirium is -2.7 MMSE points, or -0.82 standard deviation units. McCusker et al (McCusker 2001) report a similar magnitude of decline for delirious patients (-3.3 MMSE points). Extrapolating the more conservative Francis et al estimate to 18 months (the follow-up interval for the current study), leads to a net difference of -0.61 SD units for persons with delirium. For power calculations we use a worst case scenario using only those subjects with observations at all follow-up times. We expect that an initial cohort of 500 participants will be hospitalized and undergo surgery. Using attrition and refusal rates derived from our previous studies in similar study populations, we expect the number of subjects with complete observations at 18 months to be 400 [Note: we do not intend to use a list-wise complete analysis framework, but such a framework serves as a conservative lower bound for estimates of statistical power relative to more powerful and appropriate methods taking a principled approach to missing data]. Assuming (1) 25% of hospitalized elders in our cohort experience delirium during hospitalization and (2) Type-I error of 5%, we estimate that we will have 100% power to detect an effect as large as -0.61 SD units. We will have >80% power to detect effects as small as -0.33 SD units. The minimal detectable effect size lies between what are classified as small (ES = -0.20) and medium (ES = -0.50) effect sizes in Cohen's taxonomy (Cohen 1988). Medium and larger effect sizes are suggested as the lower bound of effects that are of clinical significance (Cohen 1988, Norman 2003). Therefore, despite anticipated attrition, we will have excellent power to detect our hypothesized effect. While confounders may weaken the effect size, we still have >80% power to detect a reduction of effect size by as much as 46% (to -0.61 relative to -0.33).

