
For secondary analyses, we propose to examine the cognitive trajectory up to 36-month follow-up. Prorating the Francis estimate to 36 months, yields a net difference of -1.5 SD units for persons with delirium. A conservative estimate on statistical power can be based on the anticipated complete sample of 53 of the 500 surgical patients available at follow-up month 36 (213 are censored due to truncated follow-up; the rest due to death and other losses). Assuming a cumulative incidence of delirium of 25% and a Type-I error of 5%, we estimate that we will have 99% power to detect an effect as large as -1.5 SD units; we will have >80% power to detect effects of -0.91 SD units. Thus, despite attrition, we anticipate good power to test our secondary aims.

Sample Size for the Nonsurgical Comparison Group: The nonsurgical comparison group (N= 120) is utilized only by Projects 1 and 4. Its main purpose is to quantify normal age-related changes, and to quantify retest (learning) effects on cognitive testing over time. The sample size is justified in that with N=120, assuming a large correlation ($r=.80$) of baseline and repeat testing, and a moderate retest effect (standardized difference of 0.50 units), the probable (standard) error of the mean retest effect is about 10% of a standard deviation. This level of precision is sufficient to quantify the magnitude of retest effects, which are not a primary focus but important to define and statistically isolate from the other main effects (surgery, delirium and their interactions with longer-term decline).

Similar studies have also used samples of 120 as comparison groups

B.1.1.2 Sample Size for Project 1 Sub-study: Our goal is to enroll 240 patients with or without cognitive decline for this sub-study. For the clinical outcomes sub-study, over the next year, we anticipate a total of 256 patients will reach the 6-, 12-, or 18-month follow-up assessments. We estimate that 25-50 patients, or 10-20% of those achieving the 6-18 month follow up thresholds, will meet the above criteria and require clinical examinations over the supplement year. The 10-20% figure is considered to be a reliable estimate based on prior studies in the literature (Bickel 2008,, as well as our preliminary experience using our primary cognitive outcome, the general cognitive performance measure (GCP), where we find that of 45 study subjects who have completed 6 months of follow-up, 13% show a reliable decline in cognitive performance

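### The protocol's own proration gives -1.23 SD at 36 months, not -1.5 (power about 97%, not 99%), and the 213 patients counted as truncated do not fit the stated timeline

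*Protocol*

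**What the plan says.** Protocol section B.1.1 takes its effect size from a published cohort of medical inpatients. The delirium group "declined over 2 years on MMSE performance from a baseline mean (SD) of 27 (3.3) to 23.7 (5.1"), and "a control sample declined from a baseline mean of 27 (2.4) to 26.4 (4.2"). From these it concludes: "The net decline attributable to delirium is -2.7 MMSE points, or -0.82 standard deviation units". It extrapolates this to -0.61 SD at 18 months for the primary power calculation.

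For the secondary analysis it says that prorating the same estimate to 36 months "yields a net difference of -1.5 SD units for persons with delirium". Power is based on "53 of the 500 surgical patients available at follow-up month 36 (213 are censored due to truncated follow-up", with the remaining losses put down to death and other causes). The stated results are 99% power at -1.5 SD and more than 80% at -0.91 SD, with 25% delirium and a 5% type I error. The section concludes that power for the secondary aims is good.

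Section A.2 sets the study calendar as 6 months of start-up, "30 months for patient enrollment, 42 months (additional) to complete all patient follow-ups", and 6 months of analysis. Each patient is followed for at least 18 and up to 72 months, later extended to 12 years.

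**The concern.** Two inputs to the 36-month paragraph do not follow from the rest of the document.

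- **Effect.** The 18-month and 36-month figures are both presented as scalings of one estimate, but the same scaling does not produce both. The 99% power is tied to the larger effect.
- **Sample.** If enrolment lasts 30 months and follow-up runs another 42, even the last patient enrolled can reach month 36. A count of 213 patients truncated before then does not fit that calendar.

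What is at stake is the accuracy of the stated assumed effect, power and available sample for a named secondary analysis. No design decision or primary inference depends on them.

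**Working it through.** **Inputs.** From section B.1.1: the source means and SDs quoted above, 25% delirium, 5% type I error, 400 complete patients at 18 months out of 500, and 53 complete with 213 truncated at 36 months. From section A.2: the calendar. The document does not state sidedness; two-sided is assumed because it reproduces the stated figures. Power is for a two-sample comparison of means (noncentral t, with the normal approximation alongside where given).

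**1. Reproduce the 18-month figures.**
- Net change: (23.7 - 27) - (26.4 - 27) = -3.3 + 0.6 = -2.7 points.
- In SD units: -2.7/3.3 = -0.818, the stated -0.82.
- At 18 months: -0.818 x 18/24 = -0.61, as stated. The proration is therefore linear in time.
- Power with 100 v 300: 99.95% at 0.61 SD and 81% at 0.33 SD. Both statements reproduce.

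**2. Apply the same rule at 36 months.**
- -0.818 x 36/24 = -1.23 SD. Doubling the rounded 18-month value gives -1.22.
- The stated -1.5 is larger by 1.5/1.23 = 1.22, or 22%.
- Other standardisers do not yield -1.5: the control baseline SD gives -1.69, the pooled baseline SD -1.40, and the follow-up SDs -0.79 to -0.96.
- The delirium group's gross decline does give it (3.3/3.3 x 1.5 = 1.5), but that is not a net difference from controls.

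**3. Power with 53 patients.** 25% of 53 is about 13, so 13 v 40.
- At -1.5 SD: 99.6% (t), which reproduces the stated 99%.
- At -1.23 SD: 96.6% (t) or 97.1% (normal), about 97%.
- At -0.91 SD: 79.9% (t) or 81.3% (normal). The 80% detectable effect by t is 0.912 SD. The stated 0.91 holds for this sample size and does not depend on the proration.

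**4. The timeline.**
- 6 + 30 + 42 + 6 = 84 months, the stated 7 years; 30 + 42 = 72 months, the stated maximum follow-up. The calendar is internally consistent.
- On it, the last patient enrolled has 42 months of potential follow-up, so truncation before month 36 would be 0, not 213.
- A shorter design gives a count close to 213. Assume uniform accrual over 30 months, the shortest follow-up at 18 months, and a constant loss rate of 20% per 18 months. About 215 patients are then truncated before month 36. The same assumptions leave about 128 complete rather than 53, so they explain the truncated count only.

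**5. What the complete sample might be without truncation.** Other losses in the plan are 500 - 53 - 213 = 234, out of 500 - 213 = 287 not truncated.
- If 53/287 (18.5%) retention applied to all 500: about 92 complete, detectable effect 0.68 SD.
- If 80% retention per 18 months continued: 500 x 0.80 x 0.80 = 320 complete, detectable effect 0.36 SD.

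These bounds are illustrative. The document does not say which loss rate applies beyond 18 months.

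**The case against.** The strongest reply is that nothing of substance changes. Power at the corrected effect with 53 patients is still about 97%. The 0.91 SD detectable effect is right for that sample size. A sample that is too small errs on the cautious side, and the protocol itself calls the estimate conservative and does not intend a complete-case analysis. All of this stands, and it limits the point to a minor correction.

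It can also be said that section A.2 twice gives an 18-month minimum follow-up, and section A.1 gives a range of 18 to 72 months. If 18 months were the actual shortest follow-up, some truncation before month 36 would be possible. This stands in part. The 30 + 42 month calendar is the more specific statement and adds up exactly, but the 18-month floor stays in the text. The supportable claim is that the sections conflict, not that one rules the other out.

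Three stronger readings are tempting and not supported:
- A reader might add the 213 back to the 53, get 266 complete patients and a detectable effect of about 0.40 SD, and call the sample understated five-fold. That assumes none of the 213 would die or drop out, while the plan loses 234 of the other 287. The illustrative range is 92 to 320, which is about 1.7 to 6 times 53.
- A reader might apply the 46% reduction discussed at 18 months to -1.23 SD, giving about -0.66 SD and 53% power with 53 patients. The 46% is the margin from 0.61 to 0.33 SD that 400 patients can absorb. The plan does not assume it as attenuation at 36 months, and the calculation also relies on the doubtful 53.
- A reader might conclude that the paragraph presents the 36-month analysis as able to detect only very large effects. It concludes that power is good.

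**Conclusion.** The point holds as a minor error. The 36-month effect is misstated: the protocol's own linear rule gives -1.23 SD, not -1.5, and power with 53 patients is about 97% rather than 99%. This follows from the document's figures alone, apart from the two-sided test.

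The 213 truncated patients conflict with the calendar in section A.2. The 53 looks like a leftover from a shorter design. That is an inference, because the 18-month minimum is still in the text, so the sections need to be reconciled. The size of the corrected sample cannot be fixed from the document, since it depends on a loss rate that the document does not give.

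The conclusion of good power for this secondary analysis stands, and the primary 18-month calculation reproduces and is unaffected.

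**What to change.** In section B.1.1, restate the 36-month effect as -1.23 SD and the power with 53 patients as about 97%. The 0.91 SD detectable effect can stay for as long as 53 does.

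Then reconcile section A.2 with section B.1.1: say whether any patient can be truncated before month 36 under the current timeline, and what the 18-month minimum means alongside the 42 additional months. Recompute the expected complete sample and detectable effect on that basis, stating the loss assumption after 18 months. The 92 and 320 above show how much that assumption matters and are not proposed replacements; nor should 266 or 0.40 SD be adopted.

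The cost is one rewritten paragraph and a clarifying sentence on follow-up. Study conduct, data collection and the primary analysis do not change.
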